- Compare of the incidence of symptomatic SARS-CoV-2 infection including SARS-CoV-2 related hospitalization and/or SARS-CoV-2 related death between patients treated with chemotherapy only, immunotherapy only, targeted therapy only or other/combination therapy only over 12 months post-baseline.
- Compare the serum concentration of AZD7442 at 1, 3, 6, 9 and 12-months post-baseline between solid tumor and hematologic malignancy patients.
- Compare the serum concentration of AZD7442 at 1, 3, 6, 9 and 12-months post-baseline between patients treated with chemotherapy only, immunotherapy only, targeted therapy only or other/combination therapy only.
- Compare of the incidence of symptomatic SARS-CoV-2 infection including SARS-CoV-2 related hospitalization and/or SARS-CoV-2 related death to the levels of serum concentration of AZD7442 at 1, 3, 6, 9 and 12-months post-baseline in all patients.
- Compare the incidence of severe SARS-CoV-2 (pneumonia or hypoxemia, and WHO score of ≥ 5) based on the TACKLE definition between solid tumor and hematologic malignancy patients.
- Compare the incidence of severe SARS-CoV-2 (pneumonia or hypoxemia, and WHO score of ≥ 5) based on the TACKLE definition death between patients treated with chemotherapy only, immunotherapy only, targeted therapy only or other/combination therapy only over 12 months post-baseline.
- Compare the incidence of severe SARS-CoV-2 (pneumonia or hypoxemia, and WHO score of ≥ 5) based on the TACKLE definition to the levels of serum concentration of AZD7442 at 1, 3, 6, 9 and 12-months post-baseline in all patients.

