14.1 Definitions and Secondary Endpoints

Definition of SARS-CoV-2 qualifying symptoms:

SARS-CoV-2 qualifying symptoms are based on the definitions in the AstraZeneca PROVENT trial. In combination with a positive SARS-CoV-2 antigen test, symptomatic infection includes at least one of the following symptoms and duration:

- No minimum duration
 - Fever, shortness of breath, difficulty breathing, new onset confusion (only for patients ≥ 60 years), appetite loss or decrease food intake (only for patients ≥ 60 years), increased supplemental oxygen requirement (only for patients ≥ 60 years on baseline supplemental oxygen)
- Must be present for ≥ 2 days
 - Chills, cough, fatigue, muscle aches, body aches, headache, new loss of taste, new loss of smell, sore throat, congestion, runny nose, nausea, vomiting, diarrhea

Secondary Endpoints will include the following:

- Incidence of symptomatic SARS-CoV-2 infections including but not limited to those with SARS-CoV-2 related hospitalization and/or SARS-CoV-2 related death compared between solid tumor and hematologic malignancy patients.
- Incidence of symptomatic SARS-CoV-2 infection including but not limited to SARS-CoV-2 related hospitalization and/or SARS-CoV-2 related death compared between patients treated with chemotherapy only, immunotherapy only, targeted therapy only or other/combination therapy only over 12 months post-baseline.
- Serum AZD7442 concentrations at 1, 3, 6, 9 and 12-months post-baseline compared between solid tumor and hematologic malignancy patients.
- Serum AZD7442 concentrations at 1, 3, 6, 9 and 12-months post-baseline compared between patients treated with chemotherapy only, immunotherapy only, targeted therapy only or other/combination therapy only.

- Correlation of the incidence of symptomatic SARS-CoV-2 infection including but not limited to those with SARS-CoV-2 related hospitalization and/or SARS-CoV-2 related death to the levels of serum concentration of AZD7442 at 1, 3, 6, 9 and 12-months post-baseline in all patients.
- Incidence of symptomatic SARS-CoV-2 infection including but not limited to SARS-CoV-2 related hospitalization and/or SARS-CoV-2 related death compared between patients currently on active treatment, ≤ 3 months post-treatment and > 3 months and ≤ 12 months post-treatment regardless of treatment strata.
- Incidence of Severe SARS-CoV-2 (pneumonia or hypoxemia) and WHO score of ≥ 5 compared between all four strata

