
17.0 Statistical Considerations
	
17.1 Sample Size Estimation
 
This program will recruit approximately 1,500 treated cancer patients divided into approximately 1,200 qualified solid tumor and 300 qualified hematologic malignancy patients from approximately 75 hematology/oncology medical practice locations throughout the United States. It is expected that on average, each site will enroll 16 solid tumor and 4 hematologic malignancy patients.
 
17.2 Sample Size Power
 
With a sample size of 1500 patients, the power to detect a non-inferiority margin of 5 mcg/ml with a standard deviation of 25 mcg/ml and Type I error rate of 1% is estimated to be approximately 80% when comparing the serum concentration levels between solid tumor and hematologic malignancy groups. The assumed comparison is between 1200 solid tumor and 300 hematologic malignancy patients. A target sample of 1500 patients will provide adequate size to analyze all of the secondary endpoints identified in the baseline and follow-up patient experience/COA surveys and the QoL surveys.
 
At the time of interim analysis, the power to detect a 5 mcg/ml non-inferiority margin with a standard deviation of 25 mcg/ml and Type I error rate of 1% is estimated to be approximately 45%. This assumes a sample of 600 solid tumor and 150 hematologic malignancy patients.
 
17.3 Stratification
 
This is an open-label, pragmatic, multi-center study of participants receiving AZD7442 600 mg IM or IV for prevention of symptomatic SARS-CoV-2 infection including SARS-CoV-2 related hospitalization and/or SARS-CoV-2 related death.

Patients will be stratified based on type of cancer (solid tumor vs hematologic malignancy) with additional stratification for concomitant treatment regimen of chemotherapy only, immunotherapy only, targeted therapy only and other therapy/combination therapy. It is assumed that 80% of enrolled cancer patients will have solid tumors. Patients will be sub-stratified by: currently on active treatment, ≤ 3 months post-treatment or > 3 months and ≤ 12 months post-treatment.

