17.6 Evaluations of Primary and Secondary Endpoints

The primary and secondary endpoints will be evaluated for the intent-to-treat and per protocol patient populations. The primary comparisons will be the serum concentration of AZD7442 at Days 30, 90, 180, 270 and 360 post-baseline. Serum concentration comparisons of the log-adjusted serum AZD7442 concentration will be analyzed using linear mixed models for repeated measures. Models will include disease category, overall dose, and dose/kg accounting for concomitant treatment regimen category along with appropriate treatment and time interactions. An unstructured covariance matrix will be assumed, however, in the event of non-convergence, compound symmetry, and AR (1), covariance structures will be attempted, in that order. The Least Square Means Differences, and their 95% CIs, will be reported for each timepoint (e.g., Days 30, 90, 180, 270, and 360 post-treatment).

Additional comparisons for Quality of Life (QoL) will be made between the disease category cohorts and concomitant treatment regimen categories. The disease category cohorts are solid tumor cancers and hematologic cancers. Concomitant treatment regimen categories will be defined as chemotherapy only, immunotherapy

only, targeted therapy only, other therapy/ combination therapy only. Differences in the primary endpoints will be assessed using a two-sided statistical significance level of 0.01, adjusting for planned multiple comparisons. All other differences will be assessed using a two-sided statistical significance level of 0.05.

The secondary endpoint comparisons will be made:

- between concomitant treatment regimen categories and
- between disease category cohorts

The between concomitant treatment regimen categories will account for the between disease category analyses. These secondary endpoint comparisons will be made using a logistic regression or linear mixed model accounting for potential patient and disease factors where appropriate. Additional secondary endpoints are as noted previously. The secondary endpoints will be analyzed for the Intent-To-Treat (ITT) population with a Per-Protocol (PP) sensitivity analysis.

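### The solid tumor versus hematologic serum-concentration contrast, the only comparison with a power statement, can be read as tested at 0.01 or at 0.05

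*Protocol*

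**What the plan says.** Protocol 17.6 sets two significance levels. For the first: "Differences in the primary endpoints will be assessed using a two-sided statistical significance level of 0.01, adjusting for planned multiple comparisons". For the rest: "All other differences will be assessed using a two-sided statistical significance level of 0.05".

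The passages that bear on the rank of the solid tumor versus hematologic contrast in serum AZD7442 are these.

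- **3.1 and 13.1** (primary objective and endpoint): serum concentration at five visits in all patients. No comparison between groups is mentioned.
- **3.2** (secondary objectives): "Compare the serum concentration of AZD7442 at 1, 3, 6, 9 and 12-months post-baseline between solid tumor and hematologic malignancy patients".
- **14.1** (secondary endpoints): "Serum AZD7442 concentrations at 1, 3, 6, 9 and 12-months post-baseline compared between solid tumor and hematologic malignancy patients".
- **15.1** (interim analysis): the interim primary endpoint is serum concentration, with comparisons between disease categories.
- **17.2** (power): "Type I error rate of 1% is estimated to be approximately 80% when comparing the serum concentration levels between solid tumor and hematologic malignancy groups". It adds: "The assumed comparison is between 1200 solid tumor and 300 hematologic malignancy patients".
- **17.6** (evaluation): serum concentration at Days 30, 90, 180, 270 and 360 is called the primary comparison set, and disease category is a term in the mixed model. On reporting: "The Least Square Means Differences, and their 95% CIs, will be reported for each timepoint". The same section then lists disease category cohorts among the secondary endpoint comparisons.

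**The concern.** The same contrast, on the same variable at the same five visits, is assigned to two ranks, and 17.6 attaches a different significance level to each. No sentence says which level governs.

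This matters because it is the only comparison with a power statement, and section 2.2 states a hypothesis about it: that concentrations will not differ between the two cancer groups. A p-value of 0.03, for example, would count against that hypothesis under the secondary level and leave it standing under the primary one. The study is open-label and looks at this contrast at the interim, so a level left open in the protocol could be settled after data have been seen.

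**Working it through.** **1. The passages side by side**

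| Reading | Support | Level |
|---|---|---|
| Primary | 17.6 primary comparisons, with disease category in the model; 17.2 sized at 1%; 15.1 for the interim | two-sided 0.01 (17.6) |
| Secondary | 3.2; 14.1; secondary list in 17.6 | two-sided 0.05 (17.6) |
| Neither | 3.1 and 13.1 have no group comparison | none |

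If the secondary reading is adopted throughout, 17.2 still sizes the contrast at 1% while 17.6 would test it at 5%. The disagreement remains on either reading.

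**2. Reproducing the stated power**

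Inputs from 17.2: margin 5 mcg/ml, SD 25 mcg/ml, 1,200 versus 300 patients at the end and 600 versus 150 at the interim, Type I error 1% with sidedness not given. Stated power is about 80% and about 45%.

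- Final: SE = 25 × √(1/1200 + 1/300) = 1.614 mcg/ml; 5 / 1.614 = 3.098.
- Interim: SE = 25 × √(1/600 + 1/150) = 2.282 mcg/ml; 5 / 2.282 = 2.191.
- Power = Φ(5/SE − z), normal approximation.

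| Level | z | Final | Interim |
|---|---|---|---|
| One-sided 0.01 | 2.326 | Φ(0.772) = 78.0% | Φ(−0.135) = 44.6% |
| Two-sided 0.01 | 2.576 | Φ(0.523) = 69.9% | Φ(−0.385) = 35.0% |
| Two-sided 0.05 | 1.960 | Φ(1.138) = 87.3% | Φ(0.231) = 59.1% |

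The stated figures fit one-sided 0.01: closely at the interim, and about two points short of 80% at the end. They fit neither of the two-sided levels in 17.6. The power section therefore does not settle which of those levels was meant.

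**3. Size of the gap, on the raw scale**

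- Smallest observed difference significant at two-sided 0.05: 1.960 × 1.614 = 3.16 mcg/ml.
- Smallest observed difference significant at two-sided 0.01: 2.576 × 1.614 = 4.16 mcg/ml.

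The chance that the result falls between these values is the difference between the two rejection probabilities:

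| True difference (mcg/ml) | Reject at 0.05 | Reject at 0.01 | In the gap |
|---|---|---|---|
| 0 | 5.0% | 1.0% | 4.0% |
| 2 | 23.6% | 9.1% | 14.6% |
| 3 | 46.0% | 23.7% | 22.3% |
| 5 | 87.3% | 69.9% | 17.3% |

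(Gap figures are taken before rounding.) These numbers treat the contrast as a single unadjusted comparison of means at one visit.

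**4. What the multiplicity phrase could do**

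Section 17.6 ties the 0.01 level to planned multiple comparisons without saying how. It may be the already adjusted level (0.05 / 5 visits = 0.01) or a level to be split again. If split over five visits, which is an assumption, the per-visit level is 0.01 / 5 = 0.002, power at 5 mcg/ml is 50.3%, and the disputed p-value range becomes 0.002 to 0.05.

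**The case against.** The strongest reply is that the endpoint hierarchy is clearer than it looks. The sections that formally classify endpoints for the final analysis put this contrast in the secondary list, and 17.6 itself names disease category cohorts under the secondary comparisons. Section 17.2 never uses the word primary, and 15.1 speaks only of the interim. Sizing a largely descriptive study on a secondary contrast at a strict level is not a contradiction in itself.

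Much of this stands. A reader might infer that the contrast simply is the trial's primary comparison. The documents do not support that: it is an inference from the matching 1% level and from the way 17.6 describes its primary comparisons and model. But the reply does not remove the problem, because an all-secondary reading leaves 1% in 17.2 against 5% in 17.6.

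Two further inferences should also be resisted.

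- A reader might take the 95% intervals as evidence for the 0.05 level. Section 17.6 does not say which least-squares-means differences they belong to, and 17.7 promises 95% intervals for all measurements, so they point to neither level.
- A reader might take 3.16 to 4.16 mcg/ml as the actual disputed range. Section 17.6 plans a covariate-adjusted repeated-measures model on log concentration, and 17.2 speaks of a non-inferiority margin and not of a test of difference. The band only shows the order of size.

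**Conclusion.** The point holds as an inconsistency of rank and level: one contrast, two significance levels, and no statement of which applies. A p-value between 0.01 and 0.05 could be reported either way. The nominal false-positive rate differs five-fold between the readings (0.05 / 0.01), and power at 5 mcg/ml differs by about 17 points (87.3% against 69.9%). Neither two-sided level returns the stated 80% or 45%.

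The textual conflict needs no assumption about scale. The numbers rest on the raw-scale inputs of 17.2, full enrolment with no missing values, a single visit and no further split of the 0.01. A statistical analysis plan may resolve the choice, but it would have to override one of the protocol's own statements to do so. Nothing in the protocol suggests that the ambiguity is deliberate. It should be corrected, but it does not undermine the design.

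**What to change.** Assign the contrast one rank and one significance level. State whether the test is one- or two-sided and whether 0.01 is already the multiplicity-adjusted level. Then make 3.1, 3.2, 13.1, 14.1, 17.2 and 17.6 agree. Any of three routes is coherent:

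- **Primary, two-sided 0.01.** Add the contrast to 3.1 and 13.1. Remove it from 3.2, from 14.1 and, for serum concentration, from the secondary list in 17.6. Report an interval at the level of the test (99%, if 0.01 is not split further). Restate power as about 70% final and 35% interim.
- **Non-inferiority, one-sided 0.01.** State this in 17.6, which currently plans two-sided tests of difference, and make the rank agree across the listed sections. Power is then about 78% and 45%.
- **Secondary, two-sided 0.05.** Leave 3.2 and 14.1 as they are, say in 17.6 that the primary level does not apply to this contrast, and restate 17.2 at 5%: about 87% and 59%.

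The cost is wording. Keeping two-sided 1% also means intervals about 31% wider than the 95% ones (2.576 / 1.960 = 1.31) and a stated power about ten points below the present figure.

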17.7 Descriptive Statistics

Descriptive statistics will be generated for all primary, secondary, and outcome measurements. Ninety-five percent (95%) confidence intervals will also be provided.

17.8 Immunologic Sub-Study

In the immunologic sub-study, pre-specified analyses will evaluate CD4 T-cell and CD8 T-cell data including Polyfunctional Strength Index at Day 30 post-baseline in all 1,500 cancer patients and then compare these results against similar T-cell data for any patient who tests SARS-COV-2 RNA by RT-PCR positive at any timepoint post-baseline. In addition, results will be compared to prior data for these tests obtained from normal healthy donor subjects.

Relationships between AZD7442 serum concentration, RBD-IgG antibody level and T-cell function will be assessed as described in Section 10.2

Lab data will be extracted from the nearest time point to the blood draw associated with T-cell assay testing . An unpaired Wilcoxon-test will be used to determine the statistical difference between (1) WOS \leq 2 and WOS = 3-4 and (2) WOS = 3-4 and WOS = 5-8 and (3) WOS \leq 2 and WOS \geq 3. Spearman correlation coefficient will be

calculated to observe the associations between clinical data and WOS disease severity. In the current study, baseline T-cell polyfunctionality and PSI will be determined at two timepoints in immuno-compromised cancer patients: 30-days after initial administration of AZD7442 and in temporal proximity to the time that a patient has confirmed SARS-CoV-2 by RT-PCR evidence of SARS-CoV-2 infection.

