	
antibodies, in particular subjects with a history of cancer who were treated with chemotherapy, immunotherapy, targeted therapy, other therapy or combination therapies.
 
Evaluations of real-world evidence are becoming increasingly important to healthcare providers and payers. These data analyses and interpretations are evolving in a direction that has the potential to become the standard for post-approval medication/vaccine evaluation including both comparative effectiveness and safety. In this program, the population will be broadly diverse with respect to age, gender, race, geography, socio-economic status, health literacy, and insurance coverage. This will allow for recruitment of patients considered to be comparable to those studied pre-approval but inclusive of the diverse nature of cancer patients.
 
The program population will include a large number of patients with co-morbidities that may have a significant impact on their ability to maintain therapeutic levels of AZD7442 over 12 months post-baseline and, as a result, prevent a symptomatic SARS-CoV-2 infection.
 
1.3 Rationale for Immunological Profiling Using T-Cell (Thymocyte Derived Lymphocyte) Functional Testing in Immuno-Suppressed Cancer Patients
 
Post initial administration of AZD7442, breakthrough SARS-COV-2 RNA by RT-PCR positive SARS-CoV-2 infections could result from either failure of AZD742 to provide protection and/or intrinsic T-cell (Thymocyte Derived Lymphocyte) dysfunction. Relative to the latter possibility, it is known that in normal, healthy, immune-competent subjects, there is a significant T-cell response to COVID-19 virus that can result in (1) CD4 T-cell production and secretion of cytokines that activate other immune cells including B-cells, CD-8 T-cells and macrophages to combat the viral infection and/or (2) CD8 T-cell production and release of cytokines which destroy virus-infected cells by either lysis and/or apoptosis. Unfortunately, the relationship between neutralizing antibodies and T-cell activation/secretion is unknown in immuno-suppressed cancer patients at baseline as well as in response to active SARS-CoV-2 infection. As part of this program, a sub-study has been designed to provide systematic information to help address this critical issue.

2.0
	
2.1 Primary Hypothesis

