
Clinical Hypotheses to be Evaluated
	
The primary clinical hypothesis to be evaluated is that in patients treated for either solid tumor or hematologic malignancy cancer, a dose of AZD7442 600 mg IM or IV every 6 months will prevent symptomatic SARS-CoV-2 infection including SARS-CoV-2 related hospitalization and/or SARS-CoV-2 related death, independent of type of cancer therapy up to 12 months post-dose. The possibility of a break-through SARS-CoV-2 infection may be influenced by type of cancer, current cancer treatment or length of time post-baseline administration of AZD7442.
 
2.2 Serum Concentrations of AZD7442
 
We hypothesize that serum concentrations of AZD7442 will not be different between solid tumor or hematologic malignancy treatment regimens at any time point post-baseline. We believe that serum concentration of AZD7442 may be correlated with IgG antibody level to SARS-CoV-2 and CD4/CD8 level as a measurement of T-Cell function as well as symptomatic SARS-CoV-2 infection, including SARS-CoV-2 related hospitalization and/or SARS-CoV-2 related death. We also expect to find that AZD7442 side-effects will not be significantly different between the four strata of cancer therapy (chemotherapy only, immunotherapy only, targeted therapy only, other therapy/combination therapy only).
 
2.3 T-Cell Function
 
We hypothesize that T-cell function obtained at Day 30 post AZD7442 administration in cancer patients will be within the normal range compared to historical healthy control patients' CD4/CD8 data. In addition, we hypothesize that patients who experience breakthrough SARS-CoV-2 infection will have an increase in T-cell function compared to data acquired on Day 30 post AZD7442 administration and that this increase will be in the range of expected results in historical control patients.

3.0 Study Objectives
	
3.1 Primary Objective:
 
The primary objective is to quantify the serum concentration of AZD7442 at 1,3, 6, 9 or 12-months post-baseline in all qualified cancer patients treated with AZD7442 600 mg IM or IV every 6 months.
 
3.2 Secondary Objectives:
 
The secondary objectives of the study are as follows:

- Compare the incidence of symptomatic SARS-CoV-2 infection including SARS-CoV-2 related hospitalization and/or SARS-CoV-2 related death between solid tumor and hematologic malignancy patients.

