5.5 Study Activities

- All qualified patients will be treated with AZD7442 600 mg IM or IV at baseline.
- All qualified patients will complete a baseline Patient Experience/Clinical Outcome Assessment (COA) survey (Day 1) prior to treatment with AZD7442 600 mg IM or IV.
- All qualified patients will complete follow-up Patient Experience/COA surveys on days 2, 30, 60, 90, 120, 150, 180, 181, 210, 240, 270, 300, 330 and 360 post-baseline.

- All qualified patients will complete QoL assessment on days 2, 30, 90, 180, 270, and 360 post-baseline.
- All qualified patients will have serum concentration of AZD7442 obtained at days 30, 90, 180, 270 and 360 post-baseline.
- All qualified patients will have SARS-Cov-2 RBD-IgG antibody level obtained at baseline, days 90, 180, 270 and 360 post-baseline
- At Day 30 post-baseline, all patients will have blood obtained for T-cell assay. Measurements of CD4 T-cell and CD8 T-cell function will be performed.
- Blood will be obtained for repeat T-cell assay (CD4/CD8) at Day 210 post-baseline in a selected subset of 120 hematologic malignancy and 60 solid tumor patients.
- Repeat T-cell functional testing, SARS-CoV-2 RBD-IgG and serum concentration of AZD7442 will be performed in patients who become SARS-CoV-2 RNA by RT-PCR positive at approximately 10 days or according to study site guidelines after the patient develops a positive test.

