- In the event that a patient develops any symptoms that could be possibly related to SARS-CoV-2 infection at home or out of the office, the patient must immediately test themselves using the SARS-CoV-2 Home Test Kit that was given to them at enrollment or go to a facility that can perform an EUA approved Breath Test for SARS-CoV-2 infection.
- In the event a positive test from the SARS-CoV-2 Home Test Kit or EUA approved Breath Test for SARS-CoV-2 infection is recorded, the patient must go to a qualified testing center and receive a SARS-COV-2 RNA by RT-PCR nasal swab test. These include LabCorp or Quest Diagnostics or a location that uses one of these two labs for the analysis (e.g., CVS).
- A positive SARS-COV-2 RNA by RT-PCR test must be sent to a qualified genomics laboratory (LabCorp or Quest Diagnostics) for detailed virus analysis
- In the event that a patient tests positive for SARS-CoV-2 infection by SARS-COV-2 RNA by RT-PCR, the patient should be instructed to contact their oncology center immediately
- In the event that a patient tests positive for SARS COV-2 RNA by RT-PCR, the patient must have blood drawn for serum concentration of AZD7442, RBD-IgG antibody level and T-cell analysis in the office approximately 10

days after the patient reported a positive test or in whatever timeframe is the acceptable protocol for a positive patient returning safely to the office of the Investigator.

- In the event that a patient develops a SARS-CoV-2 infection with symptoms, the patient should be immediately treated in accordance with Investigator judgement. Such treatment should include the current standard of care for symptomatic SARS-CoV-2 positive infection depending upon availability of immediate treatment. Such patient will be followed until day 360 of the study with all study procedures and assessments.
- Automatic request for patient medical records, pharmacy fill/refill data and medical insurance claims data for all patients for the 12 months post-baseline will be sent and forwarded to MediMergent for analysis.

[figure not shown]
Schedule of Activities:

	Screening/ Day 1 Baseline	Day 2	Day 30	Day 60	Day 90	Day 120	Day 150	Day 180	Day 181	Day 210	Day 240	Day 270	Day 300	Day 330	Day 360
Visit Window (Days)		+5	± 5	± 5	± 5	± 5	± 5	± 5	± 5	± 5	± 5	± 5	± 5	± 5	± 5
Informed Consent	X														
Authorization for Release of Health Info	X														
Inclusion/ Exclusion	X														
CBC including Platelet Count (if necessary)	X														

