
15.0 Interim Analysis
	
the analysis will determine which group is more likely to experience such infections.
 
An interim analysis will be performed after the first 6-month assessments are completed for the first 50% of the targeted patient sample for each malignancy, i.e., 750 patients including 600 solid tumor and 150 hematologic malignancies. The primary endpoint of the interim analysis will be the serum concentration of AZD7442 for all patients with comparisons between disease categories.
 
Secondary analyses will be conducted on the following measures in all patients included in the interim analysis set:
 
 • Incidence of break-through infections in all patients and then sub-divided into solid tumor and hematologic malignancy. • Time to infection compared between solid tumor and hematologic malignancy • RBD-IgG levels for all patients with comparisons between disease category • CD4/CD8 levels for all patients with comparisons between disease category

16.0 Immunological Sub-Study Endpoints
	
16.1 Immunologic Sub-Study Endpoints
 
 • Comparison of CD4 T-cell and CD8 T-cell function in all cancer patients at 30 days post initial administration of AZD7442 to similar tests performed in normal healthy donor subjects • Comparison of the relationship between different cancer treatment regimens and T-cell function in all cancer patients at 30 days post administration of AZD7442 • Comparison of the relationship between type of cancer (solid vs. hematologic) and T-cell function in all patients at 30 days post administration of AZD7442 • Comparison of the immunologic profile relating to AZD7442 serum level and T-cell function at the time of PCR positive SARS-CoV-2 infection in all cancer patients to Day 30 T-cell functionality • Comparison of the relationship between change from Day 30 in AZD7442 serum level, T- cell function and World Health Organization Ordinal Scale

	
(WOS) for SARS-CoV-2 disease severity in all cancer patients with documented PCR positive SARS-CoV-2 infection
 
 • Comparison of the relationship between change from Day 30 in AZD7442 serum level, T- cell function and World Health Organization Ordinal Scale (WOS) for SARS-CoV-2 disease severity in all cancer patients with documented RT-PCR positive SARS-CoV-2 infection based on type of cancer treatment.

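### Section 17.8 as worded compares infected patients' T-cell values with the whole cohort's Day 30 values, while the hypothesis in 2.3 is a rise from Day 30 in the infected patients; pairing may be intended but is not stated

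*Protocol*

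**What the plan says.** - **Hypothesis (Protocol 2.3).** The statement is that "patients who experience breakthrough SARS-CoV-2 infection will have an increase in T-cell function compared to data acquired on Day 30 post AZD7442 administration". This concerns the same patients before and after infection.
- **Analysis (Protocol 17.8).** The pre-specified evaluation takes CD4 and CD8 data including the "Polyfunctional Strength Index at Day 30 post-baseline in all 1,500 cancer patients and then compare these results against similar T-cell data for any patient" in a second group. That group is defined as anyone "who tests SARS-COV-2 RNA by RT-PCR positive at any timepoint post-baseline". The Day 30 results named here are those of all patients. The only two-sample test named in 17.8 is an unpaired Wilcoxon test between WHO ordinal scale (WOS) groups. None is named for Day 30 against infection.
- **Endpoint (Protocol 16.1, fourth bullet).** It compares the serum level and "T-cell function at the time of PCR positive SARS-CoV-2 infection in all cancer patients to Day 30 T-cell functionality", without saying whose Day 30 values are meant. Change from Day 30 appears elsewhere in 4.1 and 16.1, but only in relation to WOS severity.
- **Reason to expect selection (Protocol 1.3).** Breakthrough infections "could result from either failure of AZD742 to provide protection and/or intrinsic T-cell (Thymocyte Derived Lymphocyte) dysfunction".
- **Data available.** Protocol 5.5: "At Day 30 post-baseline, all patients will have blood obtained for T-cell assay". Protocol 9.3 requires a repeat draw for T-cell analysis about 10 days after a positive test, or when the patient can safely return. Paired values are therefore scheduled.

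**The concern.** A rise in breakthrough patients is a before-and-after question. Comparing their later values with the Day 30 values of everyone mixes two things: whether T-cell function rose after infection, and whether those who became infected differed from the cohort to begin with. If patients with weaker T-cell function are more likely to break through, their lower starting level offsets a true rise and the sub-study may report no response. With no rise at all, the same contrast can show an apparent fall. Protocol 10.2 says that more severe disease may show a blunted response through T-cell exhaustion, so a masked rise could be misread as that. The infected patients' own Day 30 values also sit inside the reference group, so the two samples are not independent.

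**Working it through.** The protocol states no effect size, power or sample size for this comparison, so there is no figure of its own to reproduce.

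**Inputs**
- From the protocol: N = 1,500 with a Day 30 assay (17.8); two-sided 0.05 for non-primary comparisons (17.6).
- Assumed: n = 75 infected (5% of 1,500); log PSI standardised to SD 1; correlation ρ = 0.5 between a patient's Day 30 and infection values; a Day 30 deficit d in infected patients relative to never-infected patients; a true rise r. For the literal 17.8 contrast an unpaired test is also assumed.

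**What each contrast estimates**
- 17.8 read literally: r + (Day 30 mean of infected − Day 30 mean of all). The infected are 5% of the cohort, so the second term is −d × (1 − 0.05) = −0.95d.
- Paired change: r only.

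**Standard errors**
- Used by an unpaired test: √(1/75 + 1/1,500) = 0.118.
- Actual SE of the 17.8 difference, allowing for the overlap: √(1/75 + 1/1,500 − 2 × 0.5/1,500) = 0.1155.
- Paired change: √(2 × (1 − 0.5)/75) = 0.1155.

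**False rejection with no true rise (r = 0).** The unpaired test rejects when the absolute difference exceeds 1.96 × 0.118 = 0.232.

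| Deficit d | Expected 17.8 difference | Unpaired, normal approximation | Paired |
|---|---|---|---|
| 0 | 0 | 4.5% | 5% |
| 0.1 SD | −0.095 SD | 12% | 5% |
| 0.2 SD | −0.19 SD | 36% | 5% |
| 0.5 SD | −0.475 SD | 98% | 5% |

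For d = 0.5: (0.475 − 0.232)/0.1155 = 2.10, and Φ(2.10) is about 98%. Simulated rank-sum tests give about 5%, 12%, 35–36% and 97–98% for the four rows. Simulated signed-rank tests stay at about 4–6%.

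**Power for a true rise of 0.5 SD.** The simulated 17.8 contrast detects it in about 98% of trials at d = 0, 93% at 0.1 SD, 74% at 0.2 SD and 41% at 0.3 SD. At d = 0.5 the expected difference is 0.5 − 0.475 = +0.025 SD, and an increase is found in only 3–4%. The paired test detects it in about 99% throughout.

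**A second model.** Here infection risk depends on the underlying T-cell level, with ρ = 0.6 and 10% infected. At an odds ratio of 0.75 per SD and no rise, the 17.8 contrast averages −0.20 SD and rejects in 64% of runs; the paired test rejects in 5%. With a 0.3 SD rise the rejection rates are 19% and 97%. At an odds ratio of 0.5 and the same rise, the 17.8 difference is negative (−0.16 SD).

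**No selection.** Neither contrast is biased. At 5% infected, ρ = 0.6 and a 0.3 SD rise, power is 68% for 17.8 and 80% paired. The paired SD is √(2(1 − ρ)), so this gain is absent at about ρ = 0.5 and would turn into a small loss below it.

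**The case against.** The strongest reply is that 17.8 is loosely worded and pairing was meant all along. Much supports that:
- The figure of 1,500 may only describe who is assayed at Day 30.
- 17.8 ends by saying that T-cell function is determined at two timepoints, Day 30 and near RT-PCR confirmation.
- 5.5 calls the infection sample a repeat test.
- The fourth bullet of 16.1 fits a paired comparison, and change from Day 30 will be derived anyway for the WOS analyses.
- 17.12 leaves models for other endpoints open, including repeated-measures models, and a SAP may settle the test.
- The interpretation table announced in 10.2 is not in the text available, so what it compares cannot be checked.

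These points stand as far as intent goes. They also rule out saying that the protocol fixes an unpaired test; the rank-sum test above is an assumption. They do not remove the point, because the only reference group that 17.8 names is the whole cohort, and no section states a paired analysis of this hypothesis. The bias comes from the reference group, whatever test is used.

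A reader might also infer that infected patients do start lower, and hence that the hypothesis will be answered wrongly in any case. The documents do not support this. Section 1.3 offers T-cell dysfunction as one possible cause beside drug failure, and 2.3 expects Day 30 function in these patients to lie in the normal range. With equal starting levels the 17.8 contrast is unbiased, and the sample overlap does no material harm (rejection of 2–5%).

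**Conclusion.** The point holds as a mismatch between hypothesis and stated comparison. As worded, 17.8 estimates the true rise plus a selection term, while 2.3 concerns the rise alone. The selection term is zero only if breakthrough is unrelated to Day 30 T-cell function, and 1.3 gives a reason to doubt that without asserting it.

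The size cannot be fixed from the protocol, which gives no deficit, SD, correlation or infection rate. Under the stated assumptions the effect ranges from none to decisive as the deficit goes from 0 to 0.5 SD. The 0.5 SD figure is the far end of that range and not a forecast. The matter is confined to the immunologic sub-study and does not touch the primary serum-concentration endpoint. It is still worth correcting, because the paired contrast uses samples already scheduled.

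**What to change.** In 17.8, and in the fourth bullet of 16.1, state that the breakthrough hypothesis is tested in RT-PCR-positive patients as the change from each patient's own pre-infection Day 30 value. Use a signed-rank or paired t test on log PSI, with a confidence interval. Exclude infections that precede the Day 30 sample: 17.8 admits a positive test at any time after baseline, and for those patients Day 30 is not a pre-infection value.

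Report separately the Day 30 values of later-infected against never-infected patients. That comparison addresses the T-cell dysfunction question in 1.3.

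The cost is wording only, with no extra blood draws. The small downside is that infected patients without a valid pre-infection Day 30 sample drop out of the paired test; their number should be reported.
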